	
improvement in outcomes, but there is value in restorative therapies to help maintain functionality.
 
The Orthocor Active System delivers OrthoCor's patented Pulsed Electromagnetic Field (PEMF) therapy, a noninvasive, temporary relief for pain. The key to OrthoCor's therapy is the use of specialized PEMF technology. In particular, PEMF works at the source of injuries, and helps accelerate the body's natural anti-inflammatory and recovery responses. Inside every Active System is the OrthoCor, a microchip that delivers PEMF directly to the source of injuries. Furthermore, PEMF has been shown to stimulate reaction pathways that result in pain and inflammation reduction.

Study Assessment/ Evaluation:	Pain assessments will be conducted utilizing the Mankoski Pain Scale which will be compared to the pain assessments of subjects who were prescribed the Standard of Care (SOC) intervention.
Study Endpoints:	
Primary Safety Endpoint: The safety endpoint of this study will be the adverse events reported with the OrthoCor Active System pain after 2 weeks of use.
 
Primary Efficacy Endpoint: The efficacy endpoint of this study will be the comparison of the OrthoCor Active System pain assessment scores to the Standard of Care (SOC) intervention after 2 weeks of use.

Exploratory Assessment:	
Exploratory Assessment: The exploratory assessment of this study will be the performance of the OrthoCor Active System after an additional 2 weeks of use and is intended for research and publication only.

Number of Patients:	
Up to 100 subjects will be enrolled in order to achieve up to 50 using the OrthoCor Active System and up to 50 using the Standard of Care (SOC) intervention. The patients will be enrolled consecutively at the participant site until enrollment is met.
 
For the exploratory assessments, the 50 subjects who received SOC will have the opportunity to cross-over and use the OrthoCor Active system.

Number of Sites:	Five (5) sites are anticipated
Anticipated Study Duration:	3-5 months
Study Eligibility Criteria	
Inclusion Criteria:
 
Participants must meet ALL of the following:
 
 1. Individuals presenting with pain in superficial soft tissue, such as ankle, back, knee, wrist, elbow, shoulder, foot, or neck pain,

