8.3 Subject Population

The target population for this measurement consists of both males and females, presenting to the designated study sites with pain in superficial soft tissue, such as in the ankle, back, knee, wrist, elbow, shoulder, foot, or neck who are prescribed the use of the OrthoCor Active System or Standard of Care (SOC) intervention.

Eligible subjects must meet the inclusion and exclusion criteria described in Sections 8.4 and 8.5. Any questions from the investigative site regarding a potential subject's eligibility for enrollment must be discussed with the Sponsor (or designee) prior to consenting and enrolling the subject into the study for the investigational measurement.

It is estimated that up to 100 subjects may be enrolled into the study.

Patients will be enrolled consecutively at each participant site until up to 50 using the OrthoCor Active System and up to 50 using the Standard of Care (SOC) intervention have enrolled. The CRO will stratify the arms (OrthoCor Active System vs SOC) by selecting the arm alternatively. The patients will be enrolled consecutively at the participant site until enrollment is met.

As part of exploratory research extension, patients using the OrthoCor Active system will have the opportunity to continue on the trial for an additional 2 weeks. Participants assigned SOC have the opportunity to cross-over using the OrthoCor Active system for the additional 2 weeks. Participation in the exploratory extension is optional.

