9.5 Study Schedule of Assessments

In the evening of each day the subject should rate their pain using the provided scale and record their rating in the eDiary. Refer to Table 1 Schedule of Assessments.

Table 1. Schedule of Assessments

Assessments	Screening/Baseline (Day 0)	Day 1 - 14	Research Extension (if applicable) Day 15 – 30
Inclusion/Exclusion Criteria	X		
Demographics	X		
Surgical Date	X		
Pain Assessment	X	X	X
Self-reported Pre-Existing Conditions*	X*		
OrthoCor Active System/SOC Intervention Use		X	X
Device Information	X		
OrthoPod Information	X	X	X
Concomitant Pain Medication Use	X	X	X
Adverse Event, related to the test device		X	X
Pregnancy test for WOCBP	X		

* Information to be collected if available

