4. STUDY DESIGN

This is a prospective, multi-center, randomized, open label study that will enroll up to 100 subjects. Subjects will consist of both males and females, presenting to the designated study sites with pain in superficial soft tissue, such as in the ankle, back, knee, wrist, elbow, shoulder, foot, or neck who are prescribed the use of the OrthoCor Active System or Standard of Care (SOC) intervention.

Patients will be enrolled consecutively at each participant site until up to 50 using the OrthoCor Active System and up to 50 using the Standard of Care (SOC) intervention have enrolled. The CRO will stratify the arms (OrthoCor Active System vs SOC) by selecting the arm alternatively. The patients will be enrolled consecutively at the participant site until enrollment is met.

As part of exploratory research extension, patients using the OrthoCor Active system will have the opportunity to continue the trial for an additional 2 weeks. Participants assigned SOC will have the opportunity to cross-over using the OrthoCor Active system for the additional 2 weeks. Participation in the exploratory extension is optional.

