5. STUDY OBJECTIVES AND ENDPOINTS

The primary safety and efficacy objectives are:

Safety endpoint of this study will be the adverse events reported with the OrthoCor Active System after 2 weeks of use.

Efficacy endpoint of this study will be the comparison of the OrthoCor Active System pain assessment scores to the Standard of Care (SOC) intervention after 2 weeks of use. The primary effectiveness endpoint of this study is the change from baseline of the OrthoCor Active System compared to the SOC intervention.

The exploratory objectives, for publication only, are comparison of the performance of the OrthoCor Active System to standard of care after additional 2 weeks of use.

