7. SAMPLE SIZE

The sample size estimates are calculated assuming a binomially distributed response of improvement or no improvement. Without any a priori estimates, the most conservative estimate (widest interval) is using a baseline for the standard of care (SOC) of 50% improvement. The null hypothesis for a non-inferiority study is that the experimental treatment is inferior to the standard of care. The alternative hypothesis is that the experimental treatment is non-inferior to the standard of care.

The sample size per group is based on the comparison of two proportions with baseline proportion of 50% for the experimental treatment assuming a 50% response for SOC and a non-inferiority margin of 10% assuming 90% power. The assumed confidence is 95% or a type 1 error rate of 5%.

The study will enroll 100 subjects, up to 50 using the OrthoCor Active System and up to 50 using the Standard of Care (SOC) intervention. The patients will be enrolled consecutively at the participant site until enrollment is met. The CRO will stratify the arms (OrthoCor Active System vs SOC) by selecting the arm alternatively.

For the exploratory assessments, the 50 subjects who received SOC will have the opportunity to cross-over and use the OrthoCor Active system.

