12.2. Exploratory Endpoints

The exploratory endpoints of this study will be to compare the reduction of pain symptoms from baseline on the Mankoski Pain Scale after 4 weeks of treatment with the OrthoCor Active System device and Standard of Care.

Usage (device records use), feedback via participant diaries, usability assessment, user preferences will be summarized as descriptive statistics.

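### The exploratory 4-week comparison of device with SOC has no defined SOC group through week 4; the only SOC extension path described is optional crossover to the device

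*SAP*

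**What the plan says.** **The planned comparison.** SAP 12.2 compares pain reduction from baseline "after 4 weeks of treatment with the OrthoCor Active System device and Standard of Care". SAP 5 gives the exploratory objective as "comparison of the performance of the OrthoCor Active System to standard of care after additional 2 weeks of use". Both name SOC as the comparator.

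**The protocol's version.** The synopsis describes the exploratory assessment as "the performance of the OrthoCor Active System after an additional 2 weeks of use and is intended for research and publication only". It names no comparator. SAP 13, the place for departures from the protocol, lists none.

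**Paths after Day 14.** For the device arm, Protocol 8.3 says "patients using the OrthoCor Active system will have the opportunity to continue on the trial for an additional 2 weeks". For the SOC arm it says "Participants assigned SOC have the opportunity to cross-over using the OrthoCor Active system for the additional 2 weeks", and SAP 4 and SAP 6 agree. SAP 7 extends the offer to "the 50 subjects who received SOC will have the opportunity to cross-over and use the OrthoCor Active system". Taking part is optional, and Protocol 9.4 has subjects complete and exit after 14 days.

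**Related text.** Protocol 9.0 opens the extension to all participants for another 14 days. The extension column of Table 1 (Protocol 9.5) is headed "Research Extension (if applicable) Day 15" and runs to Day 30. SAP 12.4 calls for complete cases but says that carrying the last visit forward will be considered.

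**The concern.** A comparison of two treatments at 4 weeks needs subjects who have had 4 weeks of each. The design describes such a group for the device and none for SOC. The SAP also has no rule for subjects who switch: no second baseline, no treatment periods and no label for the resulting contrast.

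The extension results are meant for publication. An estimate reported as device versus SOC at 4 weeks would describe something else, and would probably rest on volunteers only. Carrying SOC subjects' Day 14 scores forward would fill the gap with values observed at 2 weeks and present them as a 4-week SOC result.

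**Working it through.** The documents give no sample size, power or retention figure for this endpoint, so there is no planned figure to reproduce. The check traces each treatment path and asks what the stated contrast would estimate.

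**1. Paths described (Protocol 8.3 and 9.4; SAP 4, 6 and 7)**

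| Assigned arm | Days 0–14 | Extension, if entered | If not entered |
|---|---|---|---|
| Device | device | device | exit |
| SOC | SOC | crossover to device | exit |

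No row gives SOC in both periods.

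**2. What an analysis by assigned arm estimates.** Let A be the mean change after 4 weeks of device, S the mean change after 4 weeks of SOC, and D the mean change after 2 weeks of SOC then 2 weeks of device. Let c be the share of SOC-assigned subjects in the extension who cross over. The contrast is

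A − [c × D + (1 − c) × S].

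SAP 12.2 intends A − S, which needs c = 0. The only path described has c = 1, which gives A − D; S drops out. For any c in between, the result mixes D and S in a proportion that the subjects choose.

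**3. If some SOC subjects did stay on SOC.** The documents give no share, so the shares below are assumptions. With n = 50 × share against at most 50 device subjects, the difference detectable at 80% power and two-sided 0.05, in SD units, is (1.96 + 0.84) × √(1/n + 1/50).

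| Assumed share staying on SOC | n | Detectable difference |
|---|---|---|
| 0% | 0 | not estimable |
| 10% | 5 | 1.31 SD |
| 20% | 10 | 0.97 SD |
| 50% | 25 | 0.69 SD |
| 100% (reference) | 50 | 0.56 SD |

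These figures are favourable, since they assume that all 50 device subjects also continue. They address precision only. Those who decline a freely offered device are self-selected, and allocation at Day 0 does not protect that comparison at any n.

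**4. Switches before Day 14.** Protocol 9.4 provides that, if the study is declared complete after 32 subjects per group are enrolled, remaining SOC subjects may move to the device even before reaching the extension. Such subjects may have no Day 14 score on SOC, so a fixed Day 14 baseline would not suit every crossover subject.

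**5. Length of the extension.** Table 1: 30 − 15 + 1 = 16 days. Protocol 9.0: 14 days, which would end on Day 28 (14 + 14). This discrepancy is separate from the missing comparator, but it leaves the final day of the endpoint undefined.

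**The case against.** The strongest reply is that the text never closes the door on SOC follow-up. Crossover is offered, not required. Protocol 9.0 opens the extension to everyone without making crossover a condition. Table 1 marks a combined device/SOC use row in the extension column. All of this stands. A reader might infer that every SOC subject must cross over or leave, so that the number with 4 weeks of SOC is zero by design. The documents do not support that: they do not say whether an SOC subject may stay on SOC. The Table 1 row can be read as allowing it, or simply as a shared row label. What survives is narrower: no such group is defined, secured or given an analysis rule.

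A reader might also infer that the sponsor plans a 4-week superiority claim, or that up to 50 SOC subjects will contribute device-treated scores to the SOC side. Neither is stated. SAP 12.2 says only that the arms are compared. The count of 50 would require analysis by assigned arm and crossover by all, and the SAP specifies neither. The analysed set is also unsettled, because SAP 11.3 accepts any number of extension days up to 2 weeks and SAP 12.4 leaves carrying forward open.

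Finally, the endpoint is exploratory and for publication only. That limits the consequence, but it does not make the stated contrast obtainable.

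**Conclusion.** The point holds in this form: SAP 5 and 12.2 name a 4-week device-versus-SOC comparison for which the plan provides no defined SOC group. On the one SOC extension path described, an analysis by assigned arm gives immediate against delayed device use. Any subjects remaining on SOC would be self-selected and, under the assumed shares of 10% to 50%, would number 5 to 25. The SAP also adds a comparator that the protocol synopsis does not name, without declaring the change.

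The conclusion rests on the treatment paths as written. It would soften if the documents stated that SOC subjects may be followed on SOC to the end of the extension, but the self-selection would remain. The defect should be corrected before the extension data are analysed. The 2-week primary comparison is unaffected.

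**What to change.** Align SAP 5 and 12.2 with the synopsis's device-only exploratory assessment:

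- **Device-assigned subjects who continue:** report change from Day 0 to the end of the extension, with a 95% confidence interval.
- **Crossover subjects:** report change from the last score before the switch (Day 14, or earlier for anyone who switches sooner under Protocol 9.4), next to their own change while on SOC.
- **Any between-arm contrast at the end of the extension:** label it immediate versus delayed start among those who continued, not device versus SOC. The label should make the self-selection plain.
- **Missing data:** do not carry SOC scores forward past Day 14.

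If the 4-week comparator is kept instead, record it in SAP 13 as a departure from the protocol, and state whether SOC subjects may remain on SOC in the extension and how they are analysed. Separately, reconcile the extension's end day between Table 1 and the text.

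The cost is SAP wording, plus a schedule clarification. Daily pain scores are already scheduled through the extension, so no new data are needed. The sponsor gives up the 4-week device-versus-SOC label.

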12.3. Safety Variables

This is a non-significant risk study. Because no procedures are required to perform the investigational study, safety will be monitored via the reported Adverse Events, in this study. The descriptive table of Adverse Events, within protocol, will be the extent of safety reporting.

12.4. Handling Missing Data

Only participants with complete available data will be used in the statistical analysis, i.e., a complete case analysis. For missing visits, an imputation of last visit carried forward will be considered.

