11.3 Handling Missing Data

Only subjects with non-missing data for the OrthoCor Active System or the SOC will be used in the statistical analysis, i.e., a complete case analysis.

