11.2. Analysis Population

The following analysis populations will be defined for the study:

Intent-to-Treat (ITT) Population – The ITT population will consist of all enrolled subjects that completed any treatment.

Per-Protocol (PP) Population – The PP population will consist of all enrolled subjects with 2 weeks of treatment and without any critical data missing and data collected per protocol.

Safety Population – The safety population will consist of all enrolled subjects that have had treatment with active OrthoCor Active System.

The analysis of efficacy data will be conducted on the ITT and PP populations.

All safety analyses will be performed on the safety population.

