12.6. Subject Disposition

Subjects who have signed the Informed Consent Form with available data for the will be used in the statistical analysis, i.e., a complete case analysis, for Per Protocol analysis. All subjects will be included in the Intent to Treat (ITT) analysis.

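### The SAP gives conflicting ITT sets and missing-data rules, leaves carry-forward optional, and names no primary population in an unblinded trial

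*SAP*

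**What the plan says.** **Populations.** SAP 11.2: "The ITT population will consist of all enrolled subjects that completed any treatment". SAP 12.6: "All subjects will be included in the Intent to Treat (ITT) analysis". For PP, SAP 11.2 says "The PP population will consist of all enrolled subjects with 2 weeks of treatment", and adds that no critical data may be missing. On their use: "The analysis of efficacy data will be conducted on the ITT and PP populations". Neither document calls one of the two primary.

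**Missing data.** SAP 12.4: "Only participants with complete available data will be used in the statistical analysis, i.e., a complete case analysis". Its next sentence reads: "For missing visits, an imputation of last visit carried forward will be considered". Protocol 11.3 has the first rule but not the second: "Only subjects with non-missing data for the OrthoCor Active System or the SOC will be used in the statistical analysis". SAP 12.6 gives complete case a narrower scope: "i.e., a complete case analysis, for Per Protocol analysis". SAP 13 lists no departure from the protocol.

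**Setting.** SAP 9 says that the study is not blinded. Pain is rated every evening (Protocol 9.5, Table 1, Days 1 to 14). SAP 12 plans repeated measures ANOVA with a sphericity check. SAP 7 frames the hypotheses as non-inferiority.

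**The concern.** These sections decide who is analysed and what happens to a missing score, and they cannot all be followed. Taken as written, the complete-case rule drops subjects who have usable daily scores. The other choices (which ITT set, whether to carry forward, which population leads) could be settled with allocation and scores visible, so the answer may depend on the option taken. In a non-inferiority reading this matters more, because ITT and PP can disagree and the plan does not say which conclusion stands. If missingness is related to pain and differs between arms, complete case and carry-forward are both biased.

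**Working it through.** **1. The passages side by side**

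| Question | One place | Another place |
|---|---|---|
| Who is in ITT? | SAP 11.2: enrolled, with some treatment | SAP 12.6: all subjects |
| Where does complete case apply? | SAP 12.4 and Protocol 11.3: the whole analysis | SAP 12.6: PP |
| Is anything imputed? | Protocol 11.3: no | SAP 12.4: carry-forward, optional |
| Which population is primary? | Not stated | Not stated |

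Protocol 9.2 counts everyone who signs consent as a subject, and as enrolled once eligibility is also met. Under Protocol 15.2, allocation follows enrolment and the device is then sent out. Someone allocated but never treated is therefore out of ITT under SAP 11.2 and in under SAP 12.6. Device subjects wait for delivery and SOC subjects may not, so a some-treatment condition can also remove people unequally by arm.

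**2. Subjects kept by complete case**

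The documents give no missing-data rate, so the daily miss rate m is assumed. If all 14 entries are required and misses are independent, the share kept is (1-m)^14 and the standard error (SE) grows by share^-0.5:

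- m = 1%: 0.99^14 = 0.869, SE × 1.07
- m = 2%: 0.98^14 = 0.754, SE × 1.15
- m = 5%: 0.95^14 = 0.488, SE × 1.43

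If misses cluster within subjects (beta-binomial, correlation 0.3), 95, 90 and 78% remain. If only Day 14 is required, the share is 1-m: 99, 98 and 95%, with SE at most × 1.03.

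**3. Bias of the two methods**

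Assumed simulation: 200,000 per arm; Days 0 to 14; covariance 4 × (0.45 + 0.55 × 0.8^lag); linear mean fall by Day 14 of 1 on SOC and 2 on the device, so the true difference is -1.0; unadjusted change scores. From Day 2 the daily dropout probability h follows logit(h) = logit(h0) + b × (previous day's change from baseline). With b = +0.5, subjects doing worse leave; with b = -0.3, subjects who improve leave. Monte Carlo error is about 0.01 to 0.02.

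| Who leaves | h0 | Arm | Dropout | Complete case | Carry-forward |
|---|---|---|---|---|---|
| Worse | 0.007 | SOC | 10% | -0.90 | -1.10 |
| Worse | 0.007 | Device | 8% | -1.09 | -0.89 |
| Improved | 0.007 | SOC | 11% | -1.09 | -1.03 |
| Improved | 0.007 | Device | 13% | -0.90 | -0.91 |
| Worse | 0.03 | SOC | 33% | -0.63 | -1.32 |
| Worse | 0.03 | Device | 28% | -1.27 | -0.55 |
| Improved | 0.03 | SOC | 39% | -1.32 | -1.11 |
| Improved | 0.03 | Device | 44% | -0.64 | -0.67 |
| Worse | 0.03 | Both | 33%, 28% | -0.93 | -0.89 |
| Improved | 0.03 | Both | 39%, 44% | -0.95 | -0.77 |

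With one-arm dropout at h0 = 0.007, the errors are 0.09 to 0.10 for complete case and 0.03 to 0.11 for carry-forward. At h0 = 0.03 they are 0.27 to 0.37 and 0.11 to 0.45. When subjects doing worse leave, the two methods err in opposite directions. When improvers leave, both err in the same direction.

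**4. The day count**

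SAP 10 runs treatment from Day 0, and Table 1 makes Day 0 the baseline visit. Protocol 15.2 has the device arrive 3 to 5 days after the prescription is submitted. If it is submitted on Day 0 (assumed) and the device is used from arrival, use by Day 14 is at most 14 - 3 + 1 = 12 or 14 - 5 + 1 = 10 daily sessions. Protocol 9.4 requires 14 consecutive days of use before exit. For device subjects these are different clocks.

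**The case against.** SAP 12.6 sits under Subject Disposition and has a word missing, so its all-subjects sentence could mean all members of the SAP 11.2 set. That is possible, but the text does not say it, and the link between complete case and PP is legible despite the gap.

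Missing data may also be rare. Protocol 8.5 excludes people unwilling or unable to complete the daily assessment, and Protocol 18.2 has missing data queried. This stands, and it points to the lower rows of each range. It does not settle which rule applies.

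Four stronger readings are tempting and not supported:

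- *Half the sample would be lost.* This needs a 5% daily miss rate, independent misses, and all 14 entries required. The sphericity check hints at full profiles, since the classical ANOVA drops a subject with one missing day. But complete is undefined, PP refers only to critical data, and a Day-14-only reading loses little.
- *The two methods bracket the truth.* They do so only if subjects doing worse leave. Leaving after improvement is plausible for minor strains and over-exertion.
- *Equal dropout mechanisms make the bias small.* Carry-forward gave -0.77 against -1.0 with the same mechanism in both arms.
- *No device subject could meet the PP rule of 2 weeks of treatment.* That follows only if Protocol 9.4's exit rule is ignored. The clocks conflict; the documents do not show that PP is empty.

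Nor does Protocol 9.4 let SOC subjects move to the device at will. The move depends on significant improvement being noted after 32 subjects are enrolled per group, when the study counts as completed.

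**Conclusion.** The point holds and should be fixed before database lock. The textual conflicts need no assumption: two ITT sets, two scopes for complete case, an optional imputation that the protocol lacks and SAP 13 does not list as a change, and no primary population despite non-inferiority framing.

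The size is conditional on an unknown missing-data rate and the assumed simulation model. Loss of subjects runs from negligible to about half. With a true difference of -1.0 and one-arm, outcome-related dropout, the error is at most about 0.1 at roughly 10% dropout. At roughly 30 to 45% it is about 0.3 to 0.4 for complete case and 0.1 to 0.45 for carry-forward. Its direction depends on who leaves, so it cannot be predicted from the documents.

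**What to change.** 1. Define ITT once as all allocated subjects analysed in the allocated arm. Align SAP 11.2, 12.4 and 12.6 and Protocol 11.3, and name the primary population before database lock. If the non-inferiority framing stays, report ITT and PP together and require consistent conclusions.
2. Replace complete-case ANOVA and optional carry-forward with one pre-specified likelihood-based mixed model on all available daily scores, adjusted for baseline, with the Day-14 contrast as the primary test. The statistician should pre-specify the covariance and avoid compound symmetry as the only structure. In large simulated samples with about 30% one-arm dropout (subjects doing worse leaving, three assumed true covariances), the largest mixed-model error ranged from 0.01 to 0.13 by fitted structure, with compound symmetry the worst. Complete case was off by 0.28 to 0.40 and carry-forward by 0.31 to 0.45. Dropout there depended on observed scores, which suits the mixed model.
3. Keep complete case as a sensitivity analysis and add a delta analysis for data not missing at random.
4. Reconcile the day count in SAP 10 and Table 1 with Protocol 9.4 and 15.2. State how scores are used if SOC subjects move to the device under the conditional rule in Protocol 9.4.

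The cost is wording in the sections named, one model and one sensitivity program, with no new patients or instrument. The downside is that the model assumes missing at random, which the delta analysis probes.

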9.0 SUBJECT PARTICIPATION AND STUDY DURATION

Potential study subjects are males and females presenting to the designated study sites with pain in superficial soft tissue, such as in the ankle, back, knee, wrist, elbow, shoulder, foot, or neck who are prescribed the use of the OrthoCor Active System or Standard of Care (SOC) intervention. This will be a one-time on-site visit with data collection for 14 days.

All study participants will have the opportunity to continue in the research extension with data collection for another 14 days. Participation in the exploratory extension is optional.

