11.0 STATISTICAL ANALYSIS

The primary effectiveness endpoint of this study is the change from baseline of the OrthoCor Active System compared to the SOC intervention results after 14 days.

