12. STATISTICAL ANALYSIS

The data consists of multiple repeated measures and will be checked for normalcy and sphericity, and primary analysis will consist of ANOVAs for repeated measures and with other secondary analysis as appropriate for secondary hypotheses. Nonparametric methods will be used if the data is not normally distributed.

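### SAP 12.4 adds an optional, undefined carry-forward of the last visit to a complete-case rule, and conflicts with protocol 11.3 and SAP 12.6

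*SAP*

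**What the plan says.** SAP 12.4 has two sentences. The first is "Only participants with complete available data will be used in the statistical analysis, i.e., a complete case analysis." The second is "For missing visits, an imputation of last visit carried forward will be considered." Protocol 11.3 has only the first idea: "Only subjects with non-missing data for the OrthoCor Active System or the SOC will be used in the statistical analysis", which it also labels complete case. It mentions no imputation.

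On the timing of measurements, protocol 9.0 says "This will be a one-time on-site visit with data collection for 14 days," and protocol 9.5 says "In the evening of each day the subject should rate their pain using the provided scale and record their rating in the eDiary." Table 1 in protocol 9.5 has one screening and baseline column at Day 0, then pain assessment on Days 1 to 14. The primary endpoint (protocol 11.0) is the change from baseline after 14 days, device against SOC. SAP 12 describes the data this way: "The data consists of multiple repeated measures and will be checked for normalcy and sphericity." It names repeated-measures ANOVA as the primary analysis.

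SAP 12.6 links complete-case analysis to the Per Protocol analysis and puts every subject in the ITT analysis. SAP 11.2 has efficacy analysed on both populations and does not say which is primary. SAP 9 states that the study is not blinded. SAP 13, the section for departures from the protocol's analyses, lists none.

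**The concern.** The imputation sentence is written in visits, but the primary endpoint is built from diary ratings. Neither document says that a diary day counts as a visit. Nor does either say when carry-forward would be used, in which population, or whether as the main or a supporting analysis. The wording is also optional, and the sentence before it excludes the very subjects whose data would be imputed.

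At stake is who enters the primary comparison and what score they are given. With treatment assignment known to all and no rule fixed, complete-case and carry-forward results could both be produced and one chosen afterwards. Each method can also bias the difference between arms.

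**Working it through.** There is no plan figure to reproduce. The documents give no rate of missed ratings or dropout and no expected Mankoski change. The check sets the texts side by side.

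**Step 1: the unit.** Protocol 9.0 gives one on-site visit. That it falls on Day 0 is inferred from Table 1, which has a single screening and baseline column followed by the daily diary period. Each subject should have 1 + 14 = 15 ratings, of which 14 are post-baseline.

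**Step 2: what the carry-forward sentence can mean.**

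- If a visit is an on-site visit, no later visit exists that could be missing, and the sentence is never triggered.
- If a visit is any scheduled assessment day, Days 1 to 14 all count, and the value carried forward is the last diary rating. This is the most plausible reading, given the daily schedule and the repeated-measures description in SAP 12.

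**Step 3: what the complete-case sentence does.** SAP 12.4 does not say which ratings must be present. Repeated-measures ANOVA with a sphericity check, in its standard form, needs all of them. A subject who misses one evening has 13/14 = 93% of the post-baseline ratings and is dropped.

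**Step 4: the sections together.**

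| Section | Subjects with a missed rating |
|---|---|
| Protocol 11.3 | excluded |
| SAP 12.4, first sentence | excluded |
| SAP 12.4, second sentence | perhaps imputed |
| SAP 12.6, Per Protocol | excluded |
| SAP 12.6, ITT | included, method not stated |
| SAP 13 | no departure from the protocol listed |

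**Step 5: how each route can bias the comparison.** Complete-case analysis is unbiased for the enrolled arms only if subjects with full diaries resemble the others in their arm in how pain changes. Carrying the last rating forward assumes that pain stays level after the diary stops. An assumed subject shows what that can do: baseline 6.0, falling 0.2 per day.

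- True Day-14 change: −0.2 × 14 = −2.8.
- Change with the Day-k rating carried forward: −0.2 × k.
- Shortfall in the reduction: 0.2 × (14 − k).

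| Last diary day | Complete case | Last rating carried forward | Shortfall |
|---|---|---|---|
| 3 | dropped | −0.6 | 2.2 |
| 7 | dropped | −1.4 | 1.4 |
| 10 | dropped | −2.0 | 0.8 |
| 13 | dropped | −2.6 | 0.2 |

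If pain rose after the last entry, the error would go the other way. The difference between arms is distorted when the amount or timing of missing ratings, or the course of pain, differs by arm. The table shows how the method behaves for one invented subject and does not estimate the bias in this trial.

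**The case against.** **The SAP commits to no imputation.** Complete case comes first in SAP 12.4, protocol 11.3 allows nothing else, and carry-forward is only to be considered. This stands: one cannot say that the SAP imputes. But an option with no trigger, population or role is not a pre-specified method.

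**The meaning is clear enough.** Protocol 9.0 qualifies its visit as on-site, whereas SAP 12.4 does not, and a statistician would carry the last diary rating forward. This also stands for the meaning of the word, and it is why the reading in step 2 is preferred. It does not settle where or when the rule applies.

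**The SAP can be harmonised.** SAP 12.6 could be read as complete case for Per Protocol and carry-forward for ITT. That is reasonable, but SAP 12.4 does not limit its complete-case sentence to Per Protocol, and protocol 11.3 has no such split.

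**A stronger reading is tempting.** A reader might infer that, because the only on-site visit is at Day 0, the rule assigns the baseline score to a missing Day 14 and so a change of zero, discarding the diary. The documents do not support this. Day 14 would have to count as a visit when it is missing, while Days 1 to 13 do not count when they are observed. In a repeated-measures analysis, imputation also fills the empty cell and does not delete observed ratings.

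**Conclusion.** The point holds as a gap and a conflict in the plan. SAP 12.4 joins an exclusion rule to an optional imputation that has no usable unit, population or role. It departs from protocol 11.3 without SAP 13 saying so, and it does not tell the analyst how every subject can be in the ITT analysis required by SAP 12.6. Both routes it leaves open can bias the primary comparison, in either direction.

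The size cannot be computed, because the documents give neither missingness nor effect figures. The conclusion rests on two assumptions: that the on-site visit is at Day 0, and that the repeated-measures ANOVA is run in its standard form, which needs complete records. Baseline carried forward is a strained reading, and no zero-change result should be attributed to the plan. The documents leave room for a choice after results are seen; they do not show that one was intended. The text should be corrected before the data are analysed.

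**What to change.** Replace both sentences of SAP 12.4 with:

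> The primary ITT analysis uses all observed daily eDiary ratings from all subjects in a repeated-measures mixed model that does not require complete data, with the Day-14 between-arm difference in change from baseline as the primary contrast. Missing ratings are not replaced by the Day 0 score. Complete-case analysis, and carry-forward of the last observed post-baseline eDiary rating, are sensitivity analyses only.

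Replacing only the carry-forward sentence would leave the complete-case rule in force against the new text. Align protocol 11.3 and SAP 12.6 with it, record the change in SAP 13, and name the same model in SAP 11.1 and 12, which now specify ANOVA. The mixed model still assumes that missingness depends only on what was observed, so report the number of missed ratings, and of subjects with no post-baseline rating, by arm.

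The cost is a modest edit to the SAP and protocol and one or two extra sensitivity tables. No new data are needed.
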